### **8.1 Summary**

Validation of diagnostic models will occur in subgroups according to type of center (referral center v. early pregnancy unit), as the prevalence of malignancy will likely influence performance of IOTA-ADNEX and the Modified Benign Simple Descriptors.

Validation of diagnostic models refers to:

- 1) prospective validation of the false discovery rate of IOTA ADNEX and the two-step strategy at 11-14 weeks GA (False Discovery Rate in this context is how many pregnancies with a benign mass would be referred to tertiary care);
- 2) prospective validation of IOTA ADNEX and the two-step strategy in terms of sensitivity/specificity/c-index/calibration/net benefit at 11-14 weeks GA;
- 3) prospectively validation of IOTA ADNEX and the two-step strategy to discriminate between benign and malignant adnexal masses when detected at any point during pregnancy, in terms of false discovery rate/sensitivity/specificity/c-index/calibration/net benefit.

## **9. STUDY SUPERVISION AND MONITORING**

This study does not involve any risk to the participants.

Central supervision: The IOTA Steering Committee is responsible for the protocol, quality control, advice on progress and final analysis and reporting of the study.

The study will be co-ordinated by [name], to ensure timely progress and regular participation.

Local supervision: Principal Investigators are responsible for the data collection at their centres and communication with [name].

## **10. REGULATORY ISSUES**

### **PUBLICATION POLICY**

The IOTA steering committee is responsible for publication of the data in scientific journals and will be listed as co-authors if they fulfil the requirements of authorship of the International Committee of Medical Journal Editors and in accordance with the requirements of the respective medical journal.

The chief statistician is responsible for data analysis, contributes to study design (protocol draft) and will be listed as a co-author. Principal Investigators are also co-authors, according to the number of patients they contributed to the study (depending on the journal's restriction of the number of co-authors) on condition that they contribute to writing the papers, read and approve the final version, and agree to be accountable for all aspects of the work, as defined by the International Committee of Medical Journal Editors and in accordance with the requirements of the respective medical journal.

### **INTELLECTUAL PROPERTY**

The KU Leuven VAT number BE 419.052.173, represented by its department K.U. LEUVEN RESEARCH & DEVELOPMENT, having its office in 3000 Leuven, [name], Belgium, and represented by its university hospital, UNIVERSITAIRE ZIEKENHUIZEN LEUVEN holds all intellectual property rights that might result from the IOTA project (including, amongst others, this p-IOTA). Each participating centre shall remain the owner of its source data and may utilise such data AFTER the main scientific papers of the multicentre study have been published. 2D ultrasound images, clips and 3D ultrasound volumes may be used for educational purposes outside the study, as well as in other studies.

### **ETHICS AND REGULATORY APPROVALS**

The multicentre project is first approved by the central Ethics Committee of UZ Leuven, Belgium and afterwards approved by the Ethics Committee in each investigating centre. The study will be performed in accordance with the terms of the protocol, generally accepted standards of Good Clinical Practice and the investigators will adhere to all applicable laws and regulations governing the conduct of clinical trials, including but not limited to the ICH Harmonised Tripartite Guidelines for Good Clinical Practice and the Declaration of Helsinki.

Each Participating centre shall obtain an informed consent (oral or written, depending on the applicable local legislation and local Ethics Committee requirements) for all patients prior to their enrolment and participation in the Study in compliance with all applicable laws, regulations and the approval of the (local) Ethics Committee.

The Investigator shall treat all information and data relating to the Study as confidential and shall not disclose such information to any third parties or use such information for any purpose other than the performance of the Study. The collection, processing and disclosure of encoded personal data, such as patient health and medical information is subject to compliance with applicable personal data protection and the processing of personal data and/or the privacy laws applicable to the Participating centre's location).

Sponsor is subject to the rights and obligations as ‘data controller’ set forth under the European Data Protection Directive (95/46/EC) (and upon its entry into force the General Data Protection Regulation 2016/679 (“GDPR”)) in relation to the processing of Personal Data.

Each participating centre is subject to the rights and obligations as ‘data processor’ set forth under the European Data Protection Directive (95/46/EC) (and upon its entry into force the GDPR) in relation to the processing of Personal Data.

Parties’ rights and obligations with respect to Personal Data (as defined in Appendix 6) are further detailed in Appendix 6.

### **INSURANCE**

Each participating centre is fully responsible for patient care within its own hospital in agreement with local laws. Each centre is also responsible for all legal aspects of patient care and for its own insurance for all matters related to this study as required by local laws.

#### For Belgian participating centres

Art. 29 of the Belgian Law relating to experiments on human persons dated May 7th, 2004 applies. Prior to the start of the study, the Sponsor shall enter into an insurance contract in order to adequately cover study participants from Belgian sites in accordance with art. 29 of the said law.

#### For non-Belgian participating Sites

Each Participating centre shall have and maintain in full force and effect during the term of this study (and for a reasonable period following termination of the study, adequate insurance coverage for other possible damages resulting from the study at the participating centre, as required by local law. Each such insurance coverage shall be in amounts appropriate to the conduct of the services of the participating centre under this study. The participating centre and Sponsor shall be solely responsible for any deductible or self-insured retention under any such policies.

### **FINANCIAL ASPECTS**

Gynaecological ultrasound and clinical evaluations as well as treatment and pathological diagnosis are performed in the framework of routine clinical practice and require no additional expenses. There is no financial compensation for patients, including the postpartum scan, which is standard clinical practice.

## **12. APPENDICES**

### **Appendix 1 - Ultrasound examination IOTA terms and definitions**

A standardised ultrasound examination following the IOTA protocol is carried out. All ultrasound variables are included in the dedicated software. In the database 0 always means NO and 1 always means YES.

The adnexal lesion is that part of an ovary or of an adnexal mass that is judged by ultrasonography to be not consistent with normal physiology. This can be a persistent unilocular cyst, surrounded by normal looking ovarian stroma with some follicles. In this case the whole ovary containing the cyst is the 'ovary', whereas the unilocular cyst is the 'lesion'. Both are measured and the cyst is described as being 'unilocular' and not 'unilocular-solid'. In other cases the lesion is separate from the ovary (e.g. hydrosalpinx). Again, both ovary and lesion are measured separately. In other cases no normal ovarian stroma is seen. In these cases the lesion and the ovary are undistinguishable and the measurement of lesion and ovary will be the same.

Measurements (in mm):           The ovary in two perpendicular planes  
  The lesion in two perpendicular planes

[figure not shown]
The volume of the tumour is calculated from the three diameters in two perpendicular planes by the software.

- The presence of ascites (*i.e. fluid outside* the pouch of Douglas) is noted (yes/no).
- Fluid in the pouch of Douglas is measured in the sagittal plane (the largest anteroposterior diameter is given).

- An incomplete septum (as seen in hydrosalpinges) is defined as a thin strand of tissue running across the cyst cavity from one internal surface to the contralateral side, but is not complete in some scanning planes. If a cyst only has incomplete septa, it is unilocular, despite the fact that in certain sections the cyst appears to be multilocular.
- Solid means echogenicity suggesting the presence of tissue (e.g. the myometrium, the ovarian stroma, myomas, fibromas). Blood clots can be distinguished from solid tissue by looking for internal movement when gently pushing the structure with the transducer. The presence of blood flow (with the appropriate colour Doppler settings) is diagnostic for solid tissue. The absence of flow is not diagnostic. In cases of doubt the lesion should be classified as solid.
- Solid papillary projections are defined as any solid projections into the cyst cavity from the cyst wall or septum greater than or equal to 3 mm in height

D o c

[figure not shown]

If it is uncertain whether a solid papillary projection or an incomplete septum is present, the 'worse case scenario' is used. For example, 'cogwheel excrescences' and 'beads-on-a-string' (as seen in hydrosalpinges) should be classified as papillary excrescences if their height is greater than or equal to 3 mm. The 'white ball' in a dermoid (i.e. Rokitansky node) should not be classified as a solid papillary projection.

*The 'sludge' on the internal walls of endometriotic cysts is not regarded as a papillary projection. In these cases the internal walls are usually 'irregular'.*

[figure not shown]
- The number of separate papillary projections is noted (1/2/3/more).
- The presence of flow within some of these projections is noted (yes/no).
- Solid papillary projections are described as being 'smooth' or 'irregular' (e.g. cauliflower-like - this variable will be added to CDM).

In some cases, it is difficult to judge whether it is a papillary projection and from which point to measure the projection. In these cases, it may be helpful to use an imaginary line as shown in the schematic drawing:

[figure not shown]
All lesions are qualitatively classified into one of five categories:

1. unilocular (a unilocular cyst without septa and without solid parts or papillary structures). Normal ovarian stroma is not regarded as a 'solid component' (e.g. a peritoneal cyst with one cyst locule, containing a normal ovary, is unilocular and not unilocular-solid).

[figure not shown]

incomplete septum; e.g. in hydrosalpinx)

2. unilocular cyst with solid component, i.e. a unilocular solid cyst (a unilocular cyst with a measurable solid component or at least one papillary structure). This category may include pyo- or hydrosalpinges with the so-called 'beads-on-a-string' or 'cogwheel' appearance if the solid protrusions are  $\geq 3\text{mm}$ .

[figure not shown]
3. multilocular (a cyst with at least one septum but no measurable solid components or papillary projections). The 'lesion' is measured as indicated by the arrows.

4. multilocular with solid component, multilocular solid tumour (a multilocular cyst with a measurable solid component or at least one papillary structure)

5. solid (a tumour where the solid components comprise 80% or more of the tumour when assessed in a two-dimensional section).

[figure not shown]

(solid tumour with an irregular internal cyst wall)

A solid tumour may contain papillary projections protruding into cysts.

### Quantitative assessment of morphology

[figure not shown]
- In cystic-solid tumours the largest solid component is measured separately (in three perpendicular planes). The solid component is noted as being smooth or irregular (i.e. cauliflower-like). In some cases a solid papillary projection is the largest solid component and thus the papillary projection is recorded both as papillary projection and as solid component.
- The internal wall is also noted as being smooth or irregular.

If there is a solid papillary projection, then the wall is irregular by definition.

- The external walls of tumours are not described unless they the tumour is solid.

- In case of solid tumours the description of the internal wall being smooth or irregular is usually not applicable but the outline of the tumour is described as smooth or irregular.
- If there is any irregularity in either the inner wall of any cyst or in the outer wall of a solid tumour or on the surface of a solid component, the lesion is described as 'irregular'.
- The dominant feature of the cystic contents is described as anechoic (black), low-level echogenic (homogeneous low level echogenic as seen in mucinous tumours), 'ground glass' appearance (homogeneously dispersed echogenic cystic contents, as often seen in endometriotic cysts), haemorrhagic (with internal thread-like structures, representing fibrin strands; it is possible to describe the echogenicity as star-shaped, cobweb-like or jelly-like) or mixed echogenic (as often seen in teratomas) (see images attached).

- The presence of acoustic shadows, defined as loss of acoustic echo behind a sound-absorbing structure, is noted. Solid tumours are identified by the appearance of the internal texture, by the absence of internal movement when moving the transducer or by colour Doppler imaging (presence of central flow).
- 'Ovarian crescent sign', defined as the presence of normal ovarian tissue adjacent to an adnexal tumour.
- Ultrasound evidence of metastases (e.g. "omental cake" or peritoneal tumoural implants). ("absent" or "present", mandatory new variable for phase 3 and 5)

For quality control, at least one 2D greyscale and one 2D colour representative image, as well as 3D volume must be saved. In addition, one greyscale and one colour representative video clip must also be saved. Preferably, these should be stored digitally. Photographs or video are acceptable as well.

[figure not shown]
**Modified Benign Simple Descriptors**

1. Unilocular cyst with ground-glass echogenicity in premenopausal woman with largest diameter < 10 cm
2. Unilocular cyst with mixed echogenicity and acoustic shadows in pre-menopausal woman with largest diameter < 10 cm
3. Unilocular anechoic cyst with smooth internal cyst walls and largest diameter < 10 cm
4. All other unilocular cysts with smooth internal cyst walls and largest diameter < 10 cm

**ADNEX model**

ADNEX model includes three clinical predictors and six ultrasound predictors. The clinical predictors are: age (years), serum CA125 (U/mL) and type of centre to which the patient has been referred for ultrasound examination. Type of centre has been divided into oncology centres versus other centres.

The ultrasound predictors are the maximal diameter of the lesion (mm), proportion of solid tissue (%), number of papillary projections (0, 1, 2, 3, > 3), presence of more than 10 cyst locules (yes/no), acoustic shadows (yes/no), and presence of ascites (yes/no). The proportion of solid tissue is defined as the ratio of the maximal diameter of the largest solid component and the maximal diameter of the lesion.

## Appendix 2 - Data recorded at inclusion scan

### General information

- Type of centre where scan performed: Tertiary Referral Centre / Oncology Centre with ultrasound attached / Early Pregnancy Unit
- Patient referred from: self-referral, family doctor/GP, local/district hospital, Early Pregnancy Unit, obstetrics ultrasound department, private gynaecologist
- Family history:
  - Number of first-degree relatives with ovarian or breast cancer (0-20)
- Medical history:
  - Age (years)
  - Previous oophorectomy (Yes/No); if yes, which side? (Right/Left)
  - Is this pregnancy a result of fertility treatment? (Yes/No); Which type (in vitro fertilisation, intracytoplasmic sperm injection, intrauterine insemination)?
- Adnexal mass-related (the index mass of this study):
  - Diagnosed with this mass before pregnancy (Yes/No)
  - If yes - how many months prior to today?

### Ultrasound data

- Name of the ultrasound examiner
- Date of scan
- Gestational age according to ultrasound (Weeks.... Days....)
- Ultrasound system used
- Which modality used - transabdominal or transvaginal or transrectal
- Ovarian or tubal or para-ovarian or uncertain? Left or right?

### Subjective assessment

After ultrasonographic examination of the mass the investigator gives his/her subjective assessment of the mass:

- A: Benign or Malignant (borderline / invasive);
- B: Probability of malignancy (level of certainty / confidence with the diagnosis as being benign or malignant and managing it as that):

1 = benign

2 = probably benign

3 = uncertain/not possible to classify

4 = probably malignant (borderline / invasive)

5 = malignant (borderline / invasive);

- C: *Self impression*: presumed histological diagnosis (e.g. functional cyst, haemorrhagic corpus luteum cyst, pregnancy-associated cyst, theca-lutein cyst, teratoma, serous cystadenoma, mucinous cystadenoma, serous cystadenofibroma, mucinous cystadenofibroma, fibroma, endometrioma, decidualised endometrioma, abscess, hydrosalpinx, invasive - specify type, borderline - specify type; granulosa cell tumour, dysgerminoma, other);
- D: *Management*: conservative management with ultrasound follow-up, surgery by general gynaecologist, surgery by oncological surgeon, other;
- E: (*If mass diagnosed and scanned prior to pregnancy, proceed with question; otherwise non-applicable*) Any subjective ultrasound change to adnexal mass from previous scan (*five options*): 1) yes, change noted; 2) no change noted; 3) adnexal mass no longer detectable (no ovary seen); 4) adnexal mass no longer detectable but replaced by a normal ovary; 5) unsure (comment to explain why).
- F: *Colour score of ovarian mass*: score 1, 2, 3, 4
- G: *If papillations present*: 1) number of papillations; 2) three orthogonal diameters (mm) of largest papillary projection i.e. height, base 1 and base 2; 3) smooth rounded papillations - yes / no; 4) colour in papillation - score 1, 2, 3, 4 (choose worst case scenario in case of multiple papillations).

#### ADNEX Variables

- Age
- Oncology Centre (yes/no)
- Maximum diameter of the lesion (mm)
- Maximum diameter of largest solid component
- Number of papillary projections (0, 1, 2, 3, > 3)
- Presence of more than 10 cyst locules (yes/no)
- Acoustic shadows (yes/no)
- Presence of ascites (yes/no)
- CA125 level (must be measured at 11-14 week scan and at the inclusion scan if done before 11 weeks OR after 14 weeks; it should be done within two weeks (+/- two weeks) of the scan - this must be prior to surgery, if surgery has been arranged)

#### Modified Benign Simple Descriptors (tick images)

1. Unilocular cyst with ground-glass echogenicity in premenopausal woman with largest diameter < 10 cm
2. Unilocular cyst with mixed echogenicity and acoustic shadows in premenopausal woman with largest diameter < 10 cm
3. Unilocular anechoic cyst with smooth internal cyst walls and largest diameter < 10 cm
4. All other unilocular cysts with smooth internal cyst walls and largest diameter < 10 cm

#### Ultrasound features suggestive of a complication of adnexal mass: no /yes

- pop-up list (you can select more than one):
  - Suspected torsion
  - Infection/abscess
  - Haemorrhage
  - Rupture
  - Other, please specify: ....

### Management data

- Suggested management: “What type of management do you propose for this patient based on ultrasound subjective assessment?”
  - Conservative management with one further ultrasound performed 0-90 days post-partum;
  - Conservative management with longitudinal follow-up as specified in the protocol (third arm of study - if patient consents to this);
  - Conservative management but with additional scans to the one listed in third arm of study with reason (pop-up: change in morphology, change in size, suspicion of malignancy; symptoms; other: specify);
  - Surgery by a gynaecologist or general surgeon;
  - Surgery by an oncological surgeon;
  - Other, specify

### Appendix 3 - Data recorded at follow-up scan

#### General information

- Type of centre where scan performed: Tertiary Referral Centre / Oncology Centre with ultrasound attached / Early Pregnancy Unit

#### Ultrasound data

- Name of the ultrasound examiner
- Date of scan
- Gestational age according to ultrasound (Weeks.... Days....)
  
- Ultrasound system used
- Which modality used - transabdominal or transvaginal or transrectal
- Mass detectable (yes/no; and if answer is 'yes') - pop-up: no ovary seen; ovary seen)
- Ovarian or tubal or para-ovarian or uncertain? Left or right?

#### Subjective assessment

After ultrasonographic examination of the mass the investigator gives his/her subjective assessment of the mass:

- A: Benign or Malignant (borderline or invasive)
- B: Probability of malignancy (level of certainty / confidence with the diagnosis as being benign or malignant and managing it as that):
  - 1 = benign
  - 2 = probably benign
  - 3 = uncertain/not possible to classify
  - 4 = probably malignant (borderline / invasive)
  - 5 = malignant (borderline / invasive);
- C: *Self impression*: presumed histological diagnosis (e.g. functional cyst, haemorrhagic corpus luteum cyst, pregnancy-associated cyst, theca-lutein cyst, teratoma, serous cystadenoma, mucinous cystadenoma, serous cystadenofibroma, mucinous cystadenofibroma, fibroma, endometrioma, decidualised endometrioma, abscess, hydrosalpinx, invasive - specify type, borderline - specify type; granulosa cell tumour, dysgerminoma, other);
- D: *Management*: conservative management with ultrasound follow-up, surgery by general gynaecologist, surgery by oncological surgeon, other.
- E: *Any subjective ultrasound change to adnexal mass from previous scan (five options)*: 1) yes, change noted; 2) no change noted; 3) unsure (comment to explain why).
- F: *Colour score of ovarian mass*: score 1, 2, 3, 4
- G: *If papillations present*: 1) number of papillations; 2) three orthogonal diameters (mm) of largest papillary projection i.e. height, base 1 and base 2; 3) smooth rounded papillations - yes / no; 4) colour in papillation - score 1, 2, 3, 4 (choose worst case scenario in case of multiple papillations).

**ADNEX Variables**

- Age
- Oncology Centre (yes/no)
- Maximum diameter of the lesion (mm)
- Maximum diameter of largest solid component
- Number of papillary projections (0, 1, 2, 3, > 3)
- Presence of more than 10 cyst locules (yes/no)
- Acoustic shadows (yes/no)
- Presence of ascites (yes/no)
- CA125 level (NOT TO BE MEASURED AT FOLLOW-UP SCANS)

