### ***6.2 Study flow***

**Figure 1-3** illustrate the study flow.

**First arm (*primary objective - figure 1*):** Adnexal mass scanned at 11-14 weeks. If the decision is to manage the adnexal mass conservatively, the patient is to be re-scanned once more: 0 - 90 days postpartum. In addition, the patient will be asked to enter into the third arm of the study (see below) knowing that she can opt out from that arm at any point. If she consents to participate in the third arm, she will participate in a series of longitudinal examinations as described for the third arm.

All patients with a mass detected before 11 weeks will also be scanned at 11-14 weeks and can enter all three arms of the study. In this scenario, if more than one scan is performed during pregnancy before 11 weeks, only the first of several scans before 11 weeks will be included for the second and third arms of the study (see below).

**Second arm (*secondary objective - figure 2*):** Adnexal mass is seen for the first time during that pregnancy at any gestation. If the decision is to manage the adnexal mass conservatively, the patient is to be re-scanned once more: 0 - 90 days postpartum. For patients with a mass detected before 11 weeks, see also above (they will be re-scanned at both 11-14 weeks and at 0-90 days postpartum).

In addition, the patient will be asked to enter into the third arm of the study (see below) knowing that she can opt out from that arm at any point. If she consents to this, she will participate in a series of longitudinal examinations as described for the third arm.

**Third arm (*secondary objective - figure 3*):** Patients from the first and second arms who agree to enrol into the third arm i.e. longitudinal examination of an adnexal mass during pregnancy. For the purposes of the longitudinal evaluation, the time points for the ultrasound examination are:

- initial presenting scan if <11 weeks;
- 11-14 weeks;
- 16 week scan - endometriomas ONLY;
- second trimester routine scan (18-22 weeks);
- 30-34 weeks;
- any additional scans during pregnancy which resulted in either conservative management with extra scans or surgical intervention (with reason for the extra scan or for surgery documented);
- 0-90 days postpartum.

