***If the decision is to operate after the scan at which the mass was first detected during pregnancy with no follow-up scans planned before surgery, the patient is included in the study with the final outcome being the histopathological diagnosis of the surgically removed mass (see next section).***

***If the adnexal mass is not seen at a subsequent follow-up scan but has been replaced with a normal ovary, there is no need for further follow-up scans. The final outcome is benign.***

***Patients enrolled into the study but who suffer miscarriage, ectopic pregnancy or intra-uterine death can be included in the study using same criteria as above.***

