**2) Modified Benign Descriptors and ADNEX model variables.**

***Modified Benign Simple Descriptors and ADNEX model variables will be recorded for all arms of the study but will not be used when deciding on management (Appendix 1).***

***Images of all four descriptors variables are shown and selected by ticking. The ultrasound ADNEX model variables are listed and filled in as per IOTA website and application. To ensure minimum inference, they will be recorded on a separate page from the subjective assessment on the computer software programme (Clinical Data Miner, CDM).***

***Modified Benign Descriptors and ADNEX model will not be used to guide management - only subjective assessment of the expert scanner. Therefore, participating ultrasound examiners are asked NOT to calculate the risk of malignancy using ADNEX, because the management decision should not be influenced by the results of ADNEX.***

***CA125 must be measured at the 11-14 week scan and-at the inclusion scan if done before 11 weeks OR after 14 weeks. It should be done within two weeks (+/- two weeks) of the scan - this must be prior to surgery, if surgery has been arranged.***

***If found to be pregnant again at the 0-90 days postpartum scan, the outcome will be recorded in the same manner as described above. The patient can be recruited again as a separate case, but only if the patient has presented with a new cyst.***

Retrospectively from the notes and patient's history, complications such as torsion and rupture that may have occurred will also be recorded.

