#### *Clinical Information*

As the type of centre (oncological vs non-oncological centre) is a predictive variable in the ADNEX model, this information will be filled in. An oncological centre is a tertiary referral centre with a specific gynaecological oncology unit.

The ultrasound system used, ultrasound modality (transabdominal and/or transvaginal) and the name of the ultrasound examiner will be recorded. All ultrasound examiners must have passed the IOTA certification test.

**Appendix 2** outlines the specific general patient characteristics which will be recorded at the inclusion scan.

CA125 will be analysed and recorded at the inclusion scan and at the 11-14 week scan but must not be used to guide clinical management.

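### The follow-up scan form forbids CA125 without exception, yet the protocol requires CA125 at the 11-14 week scan, which is a follow-up scan for women included before 11 weeks

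*Protocol*

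**What the plan says.** Section 6.2, under the ADNEX model variables, states: "CA125 must be measured at the 11-14 week scan". It adds a sample at the inclusion scan when that falls before 11 or after 14 weeks. On timing it says: "It should be done within two weeks (+/- two weeks) of the scan", and before any planned surgery.

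Section 6.6, Clinical Information, agrees: "CA125 will be analysed and recorded at the inclusion scan and at the 11-14 week scan". So does the Appendix 2 form for the inclusion scan: "CA125 level (must be measured at 11-14 week scan and at the inclusion scan if done before 11 weeks OR after 14 weeks".

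The Appendix 3 form for follow-up scans carries the opposite instruction in its list of ADNEX variables: "CA125 level (NOT TO BE MEASURED AT FOLLOW-UP SCANS". It names no exception. The same line stands in Appendix 4, the postpartum form.

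Section 6.1 allows recruitment at any gestational age. Section 6.2 says of women whose mass is found before 11 weeks that "they will be re-scanned at both 11-14 weeks and at 0-90 days postpartum".

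**The concern.** A woman included before 11 weeks has a later scan at 11-14 weeks for which the protocol demands a CA125 sample. If that scan is recorded on the follow-up form, the examiner is told in capitals not to take one. Both instructions cannot be obeyed.

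CA125 is one of the three clinical predictors in ADNEX (Appendix 1), and comparing ADNEX with and without CA125 is a tertiary objective and outcome (sections 3 and 7.3). A serum value not drawn within its window cannot be recovered at analysis. The gaps would also fall in one identifiable group, women whose mass was seen early, rather than at random across the cohort.

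**Working it through.** No figure in the plan is in question, so the check sets the instructions side by side and then works out the sampling window.

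**Which women meet the conflict**

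| Inclusion scan | CA125 required by sections 6.2 and 6.6 and Appendix 2 | Conflict with Appendix 3? |
|---|---|---|
| 11-14 weeks | At that scan, which is also the inclusion scan | No |
| After 14 weeks | At inclusion only; the 11-14 week point has passed | No |
| Before 11 weeks | At inclusion, and again at the later 11-14 week scan | Yes, at the 11-14 week scan |

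**Which form applies to that scan**

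The protocol has three scan forms: inclusion (Appendix 2), follow-up (Appendix 3) and 0-90 days postpartum (Appendix 4). No sentence names the form for an 11-14 week re-scan. The text nevertheless points to Appendix 3:

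- The data flow at the start of section 6.6 lists an initial scan and then follow-up scans, with no third antenatal category.
- The third-arm schedule in section 6.2 lists a presenting scan before 11 weeks and the 11-14 week scan as separate time points, so the second is not the inclusion scan.
- Section 6.2 also sets the first-detection scan apart from follow-up scans when it describes surgery "after the scan at which the mass was first detected during pregnancy with no follow-up scans planned before surgery".
- The management options in Appendix 3 include conservative management with a single further scan postpartum. That fits a woman outside the third arm, whose only scheduled scan between inclusion and postpartum is the 11-14 week re-scan.

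**Whether another sample can stand in**

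The window is 14 days either side of the scan.

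- Earliest sample that can serve any 11-14 week scan: 11+0 weeks minus 14 days = 9+0 weeks. An inclusion sample drawn before 9+0 never qualifies.
- Latest scan that a sample drawn before 11 weeks can serve: 10+6 weeks plus 14 days = 12+6 weeks.

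So an inclusion sample drawn between 9+0 and 10+6 covers only the earlier part of the 11-14 week range. A centre that notices the gap within 14 days after the scan, and before any surgery, can still draw the sample, but the Appendix 3 form does not prompt it to.

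**Size**

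The protocol does not give the share of women included before 11 weeks. The 855 women of section 8 do not supply a base: recruitment is at any gestational age, that total is built from tertiary centres, and the data from the two early pregnancy units are analysed separately. No number of missing samples, and no loss of precision, can be calculated.

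**The case against.** The best defence is that a specific rule overrides a general one. Three places give the specific rule for the 11-14 week scan, while Appendix 3 is a general form note. The term "follow-up scan" is never defined, and the Appendix 2 line mentions the 11-14 week scan separately from the inclusion scan, so the authors may never have meant it to count as follow-up. A centre that knows section 6.2 well would probably still draw the sample.

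This is a plausible account of the intent, and it makes the correction easy. It does not remove the conflict: nothing exempts the scan from the Appendix 3 line, assigns it to the Appendix 2 form or sets an order of precedence.

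One might also argue from item E on the Appendix 2 form, change since the previous scan, which carries the note "If mass diagnosed and scanned prior to pregnancy, proceed with question; otherwise non-applicable". That suggests the form was not built for re-scanning a mass first seen earlier in the same pregnancy. The argument is weak, because item E is loosely worded across the forms (Appendix 3 announces five options and lists three). The conclusion does not depend on it.

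A reader might infer that the comparison of ADNEX with and without CA125 is lost for these women. The documents do not support that. Sections 3 and 7.3 state the comparison without a time point, and CA125 at inclusion is still required and prompted for, so it remains possible at first detection.

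**Conclusion.** The contradiction stands. It is confined to women included before 11 weeks and to their 11-14 week scan. If a centre follows the Appendix 3 form, a required sample is missed unless another happens to fall in the two-week window. The consequence is fewer data for evaluating ADNEX with CA125 at 11-14 weeks, including any comparison with and without CA125 made at that time point.

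The conclusion assumes that the re-scan is recorded on Appendix 3, which the text indicates but does not state. How many women are affected depends on the unknown share included before 11 weeks and on how many centres would follow the form rather than section 6.2.

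Because the primary outcome is also set at 11-14 weeks, a reader might infer that the primary false discovery rate is compromised. That would follow only if the primary analysis used the ADNEX version with CA125, and the protocol does not say which version is primary. No claim is made there. The severity is minor to moderate.

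**What to change.** Reconcile the Appendix 3 line with sections 6.2 and 6.6 and Appendix 2, so that the form used at the 11-14 week scan carries the CA125 requirement already stated in the text. One way is to except that scan from the Appendix 3 line. Add one sentence stating which form is used for the 11-14 week scan of women included before 11 weeks.

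Appendix 4 can stay as it is, because no section asks for CA125 postpartum.

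The cost is one line on a form and one sentence in the protocol. No sample or visit is added, since sections 6.2 and 6.6 and Appendix 2 already require this measurement. The correction is worth making early, because samples missed in the meantime cannot be replaced once their window has closed.
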